Initial or repeated endodontic treatment is a surgical procedure that involves several stages and requires the use of several surgical instruments, solutions and filling materials. Several endodontic techniques exist for the preparation and filling of a root canal; these are authorized for trial purposes and practitioners shall maintain their usual practice.

The medical devices and medicines used are:

- Instruments available for shaping the canal: all types of file or broach, manual or mechanical (continuous or alternating rotation system, with or without apex locator).
- Irrigation solutions used to clean the canal:
 - Disinfectant solutions: sodium hypochlorite (NaOCI, mandatory), Chlorhexidine (not systematic),
 - Chelating rinse solutions: EDTA, HEDP, citric acid or other solutions. Solution activation techniques may vary (sonic system, ultrasound, Erbium Yag laser, other laser, other).
- A neutral, semi-solid, compactable filling material to be combined with the luting cement: a master cone of gutta-percha (single cone technique) or several cones of gutta-percha (cold lateral condensation technique).
- Watertight coronal reconstruction material: glass ionomer cement or bonded composite (the use of a temporary cement such as Cavit® is strongly discouraged and the use of IRM® cement is not authorized within the framework of this trial).

✓ Number of devices under investigation to be used and their justification.

A total of 80 patients will receive PA1704 (single dose, amount required for a monoradiculated or multiradiculated tooth) and 80 patients will receive BioRoot™ RCS (single dose, amount required for a monoradiculated or multiradiculated tooth).

Number of PA1704 MD to be used: 1 syringe of 0.5 g of cement can seal up to 5 canals. One syringe will be used for a single patient. **80 syringes will have to be used**.

Number of Bioroot™ RCS MD to be used: bearing in mind that one kit can seal 35 canals (i.e. 1 kit used for several patients) and that a vial of powder can be kept for 6 months after opening, 2 BioRoot™ RCS kits will be needed in each investigating center to cover the 9-month recruitment period.

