- **Retro-alveolar X-ray check** to evaluate the results of endodontic treatment at 24 months: 1) density of the root canal filling (radiopacity + presence of voids), 2) progress of resorption of the extruded material where appropriate, 3) apical lesion (absence/appearance/still present compared with TO) and progress of the size of an existing lesion (reduction, stabilization or increase).

Upload the 24-month follow-up retro-alveolar image to the eCRF (reminder: the entire tooth – from the *crown to the apex, including the root* – must be visible in the image; see Chapter 6.1).

— Where appropriate (in the event of the appearance of a lesion or an increase in the size of a pre-existing lesion), notification of ET failure by the investigator: schedule retreatment.

For patients in the PA1704 group whose endodontic treatment is effective at 24 months: Offer to continue clinical follow-up for up to 5 years: Inform patients about the study (dedicated information note) and provide them with a consent form.

— Complete the end-of-study form at the end of the eCRF for patients whose clinical follow-up has been completed (all patients in the BioRoot™ RCS group are followed-up with for up to 24 months, and patients in the PA1704 group who decline to continue the clinical follow-up for up to 5 years or for whom treatment failure is notified at 24 months).

PA1704 arm: V6 — Clinical follow-up visit at 3.5 years (± 6 months) — Standard practice

- **Clinical examination**: Verification of the functional status of the treated tooth and percussion test (lateral and axial),
- Recording of AEs.
- **Retro-alveolar X-ray check** to evaluate the results of endodontic treatment at 3.5 years: 1) density of the root canal filling (radiopacity + presence of voids), 2) progress of resorption of the extruded material where appropriate, 3) apical lesion (absence/appearance/still present compared with T0) and progress of the size of an existing lesion (reduction, stabilization or increase).

Upload the 3.5-year follow-up retro-alveolar image to the eCRF (Reminder: The entire tooth – from the *crown to the apex, including the root* – must be visible in the image; refer to Chapter 6.1).

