7.4. Expected drop-out rates

The study includes a 24-month follow-up for patients in the BioRoot RCS arm, and a 5-year follow-up for patients in the PA1704 arm, which may mean that some patients will withdraw or be dropped from the study. These patients will not be replaced. The calculation of the number of subjects to be enrolled allowed for a 20% increase in this number, in order to anticipate the drop-out rate at 2 years.

7.5. Procedures for taking all data into account:

Data review and database freezing: Before each statistical analysis (intermediate and final), a data review meeting will be held, attended by *at least* the sponsor and the CRO's biostatistician in charge of the statistical analysis. This will enable deviations from the protocol to be identified and categorized, so that samples of patients can be evaluated for statistical analysis. This will provide an opportunity to identify factors not initially considered that could influence the trial results and which would be worth taking into account in the analysis. At the end of the last data review meeting, the clinical database will be frozen.

Once the clinical database has been frozen, statistical analyses will be carried out by the CRO in accordance with the trial's Statistical Analysis Plan.

7.6. Definition of analysis populations:

The Tolerance population is the entire population treated with the investigational MD or the comparator MD. Patients will be analyzed according to the medical device they actually received (if a patient is randomized to one arm but receives the medical device from the other arm (allocation error), they will be analyzed according to the medical device they actually received).

The modified ITT (mITT) population is the set of patients included in the clinical trial, meeting the major eligibility criteria (see below), having been treated with one of the MDs, and for whom at least one set of performance data is available (efficacy at 6 months, 12 months or 24 months based on clinical and radiological criteria). Evaluation of breaches of the eligibility criteria will be carried out blind to whichever medical device was allocated and to post-randomization data. Patients will be analyzed according to the intention-to-treat principle, i.e. according to the medical device for which they have been randomized.

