Maximum pain in the first 7 days and time to onset of maximum pain: Description and comparison, between the PA1704 arm and the BioRoot™ RCS arm, of the maximum pain experienced during the 7 post-operative days and its time to onset by a Student, Welch or Wilcoxon test.

Intra-operative pain relief between T0 and D7: Description of painkiller classes, reasons for use, frequency of use and cumulative dose per patient over 7 days. Description and comparison, between the PA1704 arm and the BioRoot™ RCS arm, of the proportion of patients who used *oral* pain medication between T0 and D7 by Pearson's Chi-2 test or Fisher's exact test.

Description of the surgical technique: Description and comparison, between the PA1704 arm and the BioRoot™ RCS arm, of the type of anesthesia, the technique used to remove the old filling material (if root canal re-treatment only), the technique used to shape the canal, the type of disinfectant and rinse solutions used and irrigation techniques, the method of application of filling material and gutta-percha condensation, and the coronal restoration technique, by Pearson's Chi-squared test or Fisher's exact test. Intraoperative complications will be described where appropriate.

Operator comfort and satisfaction: Description and comparison, between the PA1704 arm and the BioRoot™ RCS arm, of operator comfort criteria. Satisfaction will be described at T0 and 2 years, and the proportions of satisfied operators will be compared.

For the performance criteria (efficacy rate, filling density, and material resorption) evaluated at 3.5 years and 5 years in the PA1704 arm: These criteria will only be described.

7.7.6. Safety/tolerance analysis:

The tolerance analysis will focus on the Tolerance population. Tolerance data is to be expressed as the number of adverse events (AEs) and the number of patients reporting at least one AE. Severity, cause (filling material or surgical technique) and the time of occurrence shall be described. The proportions of AEs and patients with AEs will be compared between the 2 groups. The proportions of patients who used an additional dental consultation for significant post-operative complication or pain will be described and compared, between the PA1704 arm and the BioRoot™ RCS arm, by Pearson's Chi-squared test or Fisher's exact test.

Defects in the devices will be described in the form of a list and proportions will be compared between the 2 groups.

7.7.7. Intermediate analyses:

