No interim analysis of the primary criterion is planned. The main analysis will only be carried out after the 2-year follow-up of all patients enrolled.

Two interim analyses of the secondary criteria have been planned. These will be carried out after 6 and 12 months' follow-up for all included patients.

The alpha risk will not be inflated, as the main criterion will not be analyzed in the interim analyses. Therefore, no alpha risk adjustment method is required. The final analysis will focus on the primary and secondary criteria.

For patients treated with the PA1704 ready-to-use filling material and who agree to be followed-up with for up to 5 years, a non-comparative descriptive analysis of secondary performance and safety criteria at 3.5 years and 5 years will be carried out at the end of their participation.

7.7.8. Criteria for stopping the clinical trial from a statistical point of view:

None. Interim analyses are only used to collect data on secondary criteria before the end of the study. The conclusion on the non-inferiority of PA1704 compared to BioRoot™ RCS will only be made on the final analysis at 2 years.

7.7.9. Changes to the statistical analysis plan:

The statistical analysis plan will be drawn up before the first interim analysis is carried out. The initial analysis strategy may undergo minor modifications following each data review, and the new statistical analysis plan will be described in detail at that time.

7.7.10. Specification of sub-groups for further analysis:

The following sub-group analyses will be carried out, at least on the PP population, during the final analysis at 2 years. Other factors not considered in this protocol may be added in the Statistical Analysis Plan.

- For the primary criterion, the rate of effective treatment at 2 years:
 - Prognostic factors at enrolment
 - Presence or absence of a periapical lesion,
 - Indication for endodontic treatment: initial versus repeat endodontic treatment,
 - Factors related to the surgical procedure
 - Type of rinse solution used to finalize root canal disinfection,
 - Operating techniques used: technical platform used (whether or not a microscope was used), manual files versus continuous rotation versus alternative rotation.
- Post-operative pain:
 - Operating techniques used: manual files versus continuous rotation versus alternative rotation.
 - Initial pulp pathology (pre-existing inflammatory situation or necrosis or live pulp),

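### Five-year PA1704 safety is summarised as crude AE counts and proportions, without patient-time or numbers at risk and over two unreconciled denominators

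*Combined protocol and SAP*

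**What the plan says.** - **Measure.** Section 7.7.6: "Tolerance data is to be expressed as the number of adverse events (AEs) and the number of patients reporting at least one AE". It adds: "Severity, cause (filling material or surgical technique) and the time of occurrence shall be described". In section 6.1, Table 3 lists the proportion of patients with at least one AE, assessed continuously to 24 months for BioRoot RCS and to 5 years for PA1704.
- **Population.** Section 7.6: "The Tolerance population is the entire population treated with the investigational MD or the comparator MD". Section 6.2 sets the planned PA1704 number: "A total of 80 patients will receive PA1704".
- **Late analysis.** Section 7.7.7 says that "a non-comparative descriptive analysis of secondary performance and safety criteria at 3.5 years and 5 years will be carried out", and restricts it to PA1704 patients "who agree to be followed-up with for up to 5 years".
- **Who can continue.** The V5 text in section 6.5.2 reads: "For patients in the PA1704 group whose endodontic treatment is effective at 24 months: Offer to continue clinical follow-up for up to 5 years". It requires a dedicated information note and consent form. The synopsis and the opening of section 6.5.2 make the same offer without the condition on efficacy. The synopsis also marks the 5-year visit as optional.
- **Who leaves earlier.** Section 6.3 lists a serious adverse event and a failure needing retreatment among the grounds for ending participation. Section 6.5.2 stops safety evaluation when a patient exits for failure.
- **AE contact.** There is a 7-day booklet, a day 7 call and V2 within 45 days where it is held. Visits follow at 6, 12, 24, 42 and 60 months.

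No section gives patient-time, numbers at risk, a censoring rule or a time-to-first-AE method for AEs. Section 7.7.11 plans no imputation.

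**The concern.** Section 3.3 says this is the first use of PA1704 in humans, and section 3.4 says the extension is there to supply 5-year data for CE marking and benefit-risk monitoring. No comparator is followed after 24 months, so the late AE figures must be interpretable on their own. A crude proportion is interpretable only when everyone in the denominator has been watched for the same time, and here that is not so.

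- Over all treated patients, someone who leaves at 24 months without an AE counts the same as someone seen AE-free to 5 years.
- Over patients who continue, those who left earlier disappear, together with any AE they had. A patient who exits because of a serious AE has had an AE by definition, so this omission removes events.

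Describing onset times does not resolve this, because onset times without numbers at risk give no frequency.

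**Working it through.** **1. The plan's own figure.** Section 7.2 gives 66 per group. With 90% efficacy in both arms, a 13-point margin, one-sided 5% and 80% power: 2 × 0.9 × 0.1 × (1.645 + 0.842)² / 0.13² = 65.9, so 66. Adding 20%: 66 × 1.2 = 79.2, so 80. Both figures reproduce. The plan states no AE rate and no extension number, so what follows is an illustration.

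**2. Inputs.**
- From the plan: 80 treated; 20% loss by 24 months (section 7.4), so 16 lost and 64 remaining; 90% efficacy (section 7.2, stated for BioRoot RCS and assumed equal for PA1704).
- Assumed: extension uptake u of 50–90%; a constant first-AE hazard h of 5% or 10% a year; losses spread evenly over 0–2 years; no loss within the extension; all AEs captured while a patient is followed.

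**3. Number in the extension.** n = 80 × 0.8 × 0.9 × u = 28.8 (u = 0.5) to 51.8 (u = 0.9). That is 36–65% of the 80, and the same share of possible patient-time in years 2–5.

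**4. All-treated denominator.** True 5-year risk = 1 − e^(−5h). Proportion shown = [16 × P + (64 − n)(1 − e^(−2h)) + n(1 − e^(−5h))] / 80, where P = 1 − (1 − e^(−2h))/(2h).

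For h = 0.05: P = 0.0484, 1 − e^(−0.10) = 0.0952 and 1 − e^(−0.25) = 0.2212.
- n = 28.8: (0.77 + 3.35 + 6.37)/80 = 13.1%
- n = 51.8: (0.77 + 1.16 + 11.47)/80 = 16.7%

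| h per year | True 5-year risk | Shown over all 80 |
|---|---|---|
| 5% | 22.1% | 13.1–16.7% |
| 10% | 39.3% | 24.0–30.1% |

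If the offer is not limited to effective treatment, n = 64 × u = 32 to 57.6. At h = 0.05 each extra continuing patient adds (0.2212 − 0.0952)/80 = 0.16 points, so the range becomes 13.6–17.7%.

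**5. Continuing-patient denominator.** In the same model, patients followed throughout show 1 − e^(−5h), which is 22.1% or 39.3%. The dilution disappears. What remains is selection by earlier exit, refusal and, on the V5 wording, efficacy at 24 months. The documents give nothing from which to size it.

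**6. Counts per period.** Take 0.10 AEs per patient-year, 60–100% uptake, and so 34.6–57.6 patients continuing.
- Months 12–24: 68 patients at risk on average (72 falling to 64), so 68 × 1 × 0.10 = 6.8 AEs.
- Each 18-month late period: 34.6 × 1.5 × 0.10 = 5.2, up to 57.6 × 1.5 × 0.10 = 8.6 AEs.

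The count can go either way. Divided by patient-years (68, then 51.8 to 86.4), every period returns 0.10.

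**The case against.** The best answer is that section 7.7.7 already names the late population as those who agree to continue, and no sentence says that late percentages will be taken over all 80. On that reading the shortfall in step 4 does not arise. This stands as a limit on the illustration. It does not rescue the plan: Table 3 with sections 7.6 and 7.7.6 carries the proportion to 5 years in everyone treated, and the section 7.7.7 group leaves out earlier exits.

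Other points that stand:
- Hazard and uptake are assumed. The foreseeable AEs in section 14.4 are peri-procedural, so a real decline in AE rate is plausible.
- The 20% loss and the 10% not effective may overlap, since failure needing retreatment is itself a ground for withdrawal. The 90% is on soft criteria, which count uncertain efficacy as success.
- Unfollowed patients are not wholly unseen. Section 14.2.5 asks for serious AEs within 30 days of the last visit, and for any later event the investigator thinks could be device-related. Treatment failure itself is not an AE (section 14.2.1).
- Reasons for early exit are listed (section 7.7.1), and the late analysis is descriptive with no test.
- Section 7.7 defers detail to a later SAP. That is where the fix belongs, but section 7.7.6 already sets the measure.

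A reader might go further and infer that late AE frequency must fall by construction. The documents do not support that. Cumulative figures cannot fall, counts per 18-month period need not (step 6), and the dilution requires the all-treated denominator. A reader might also infer that 18-month gaps cause late AEs to be missed. That is plausible, but the documents give no capture rate, and AEs may also be noted at unscheduled visits or reported by patients during office hours.

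**Conclusion.** The point holds in limited form. PA1704 safety to 5 years is to be summarised by crude counts and proportions over two unreconciled denominators. The all-treated figure understates 5-year risk: in the illustration, by 5.4 to 9.0 points at a 5% yearly hazard (22.1 − 16.7 and 22.1 − 13.1). That size rests on the assumed hazard, uptake and loss pattern; the direction requires only that some patients at risk of a first AE go unobserved after 24 months. The continuing-patient figure is not diluted, but it describes a selected group, by an amount that cannot be calculated here. Neither figure allows late AE frequency to be compared with earlier periods. The primary efficacy analysis is unaffected. This is a cheap improvement.

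**What to change.** In sections 7.7.6 and 7.7.7 and in the SAP, for all treated PA1704 patients:

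1. Report the number at risk, patient-years, number of AEs and AEs per patient-year for 0–7 days, 8 days–24 months, 24–42 months and 42–60 months.
2. Report the 5-year cumulative incidence of a first AE by Kaplan–Meier, censored at last AE contact, with numbers at risk and exit reasons shown.
3. State the denominator of every late AE percentage. Keep any summary restricted to continuing patients as a labelled supplement.
4. Note beside the results that censoring may be informative (exits for serious AE, failure or refusal) and that contact was sparser after 24 months. Rates per patient-year do not correct for missed events.

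The passages on who is offered the extension (V5 text against the synopsis and the opening of section 6.5.2) should also be reconciled, so that the selected group can be described.

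The cost is SAP wording, one table and one figure, from AE onset dates (section 14.2.1) and exit information already collected. The downside is an estimate that relies on a censoring assumption, which the numbers at risk and exit reasons let the reader judge.

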The clinical data collected at enrolment and at each visit, as well as variations between each occasion, if applicable, will be described in each group and in the total population. Descriptive statistics will be presented according to the nature of the criterion analyzed:

- Quantitative variable: cohort, number of missing data, mean, standard deviation, median, minimum, maximum;
- Qualitative variable: absolute frequencies (N) and relative frequencies (%) per class in each group, number of missing data.

Comparative analyses (for an NI study):

Analysis of the primary performance criterion: this will be carried out using 2 approaches, in accordance with the literature:

- **Primary soft criteria analysis**: treatment rates with complete or incomplete cure are compared against failure rates,
- **Secondary analysis of strict criteria**: treatment rates with complete healing are compared against rates of failure or incomplete healing (complete healing can take up to 4 or 5 years).

The comparison of efficacy rates between the 2 groups will be carried out using the Dunnett and Gent χ^2 test (Dunnett CW and Gent M. 1977; Elie C. et al., 2008). We will reject the null hypothesis H0 and conclude that the new PA1704 material is not inferior to the BioRoot[™] RCS reference material if the difference in 2-year efficacy rate between the 2 products is greater than the non-inferiority limit, set at 13%.

In addition, the difference in the 2-year efficacy rate between the 2 materials are to be calculated; its unilateral confidence interval of 95% will be provided and the lower limit is will be compared against the non-inferiority limit.

Additional analyses: The primary performance criterion will also be analyzed depending on covariates (prognostic factors at enrolment, factors related to the surgical procedure), including:

- Indication for endodontic treatment: initial versus retreatment,
- Diagnosis at TO: presence versus absence of apical lesion,
- Operating technique used, type of irrigation solution used to clean the root canal, technical platform (whether or not a microscope is used).

Analysis of secondary performance and safety criteria:

As a general rule, 2 independent means are compared using the Student's t-test; if the variances are unequal (verified by the Fisher's test), Welch's test will be used instead of the Student's test. If the conditions for applying the Student test are not met (n < 30), the non-parametric Wilcoxon test is used.

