7.3. Degree of significance and power of the clinical trial

The main analysis will be carried out using a one-tailed statistical test with a significance threshold α set at 5%. The clinical trial is designed to ensure 80% power for the main analysis test. Secondary analyses will be carried out using two-tailed statistical tests with a significance threshold α set at 5%.

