7.7. Statistical methods

The statistical methods are based on the following elements and will be detailed in the Statistical Analysis Plan.

7.7.1. Sample description:

The description of the subjects enrolled who completed the trial and those enrolled who left prematurely will be presented using a table of absolute (N) and relative (%) frequency. Reasons for premature discharge and deviations from the protocol will be listed.

7.7.2. Descriptive analyses:

Clinical data collected at enrolment and at each visit will be described. Descriptive statistics will be presented according to the nature of the criterion analyzed:

- Quantitative variable: sample size, number of missing data sets, mean, standard deviation, median, minimum and maximum;
- Qualitative variable: absolute frequencies (N) and relative frequencies (%) per class in each group, number of missing data.

Graphs will be provided for each variable.

7.7.3. Comparative analyses:

A comparison of 2 independent means will be made using the Student's t-test; if the variances are unequal (verified by the Fisher's test), use the Welch's test instead of the Student's test. If the conditions for applying the Student test are not met (n < 30), the non-parametric Wilcoxon test is used.

2 independent percentages are compared using Pearson's Chi-2 test. If the conditions for application are not met (at least one theoretical number < 5), Fisher's exact test is used.

7.7.4. Analysis of primary performance criterion:

As a reminder, the primary performance criterion is the efficacy rate at 24 months of treatment based on clinical criteria assessed by the investigator (tooth functionality and pain level) AND radiological criteria assessed blind by independent reviewers (complete healing, reduction of lesions, failure). In the event of failure at 6 or 12 months, the patient will be considered to have failed at 24 months.

The primary criterion will be analyzed using 2 approaches, in accordance with the literature:

- **Primary analysis of soft criteria**: treatment rates with complete or incomplete cure are compared against failure rates;
- **Secondary analysis of strict criteria**: treatment rates with complete healing are compared against rates of failure or incomplete healing (complete healing can take up to 4 or 5 years).

The comparison of efficacy rates between the 2 groups will be carried out using the Dunnett and Gent χ^2 test (Dunnett CW and Gent M 1977; Elie C et al 2008).

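### Section 7.7.6 compares proportions of adverse events between arms, but the plan's only test for percentages assumes independent units and one patient can have several events

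*Combined protocol and SAP*

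**What the plan says.** Section 7.7.6 separates two quantities: "Tolerance data is to be expressed as the number of adverse events (AEs) and the number of patients reporting at least one AE". It then plans a comparison of both: "The proportions of AEs and patients with AEs will be compared between the 2 groups". The synopsis repeats this. Neither place gives a denominator for the proportion of AEs or names a test for it. Within 7.7.6 a chi-squared or Fisher test is named only for patients who needed an additional dental consultation.

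The general rule is in section 7.7.3: "2 independent percentages are compared using Pearson's Chi-2 test", with Fisher's exact test if an expected count is below 5. The synopsis puts the same rule under the heading "Analysis of secondary performance and safety criteria", so it reaches the safety data. Section 7.3 sets secondary analyses at two-sided 5%. No method for repeated events in a patient is given.

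For defects, 7.7.6 says: "Defects in the devices will be described in the form of a list and proportions will be compared between the 2 groups". The unit is not stated. Section 6.2 assigns one PA1704 syringe to one patient. It plans BioRoot RCS supply "bearing in mind that one kit can seal 35 canals (i.e. 1 kit used for several patients"), at two kits per centre.

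**The concern.** A chi-squared or Fisher test on percentages takes each unit as one independent yes/no observation. A patient fits that description; an adverse event does not. Events from one patient tend to go together, and the number per patient can exceed one, so AEs divided by patients is not a proportion at all.

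If the general rule is followed for AEs, chance differences between the arms can reach nominal significance more often than 5% of the time. This is the first use of PA1704 in humans (section 3.3), its adverse effects are described as unknown (section 4.2), and the trial aims to show that safety is not affected by the change in presentation (section 3.4). A spurious signal in either direction would confuse that message. The two interim analyses, which the synopsis says cover safety criteria, would repeat the comparison.

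**Working it through.** **Inputs from the documents.** 80 patients per arm (section 7.2); two-sided 5% for secondary analyses (7.3); chi-squared or Fisher for percentages (7.7.3). The planned size reproduces: (1.645 + 0.842)² × 2 × 0.90 × 0.10 / 0.13² = 65.8, so 66 per group, and 66 × 1.2 = 79.2, so 80.

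**Assumptions.** The documents give no AE rate or dispersion. I take a mean m of 0.3 to 0.6 AEs per patient, a variance/mean ratio φ of 1 (Poisson) to 3, and no true difference.

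**1. Patients with at least one AE.** This is one observation per patient. Simulating the planned rule with 80 v 80 and true rates of 10, 30 and 50% gives false-positive rates of 4.8 to 5.0%. The level holds.

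**2. AE totals, with each event as a unit.** With totals A and B, the test is z = (A − B)/√(A + B). It assumes variance equal to the mean, whereas the true variance is φ times larger. The false-positive rate is therefore about 2 × [1 − Φ(1.96/√φ)]:

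| φ | 1.96/√φ | False-positive rate |
|---|---|---|
| 1 | 1.96 | 5.0% |
| 1.5 | 1.60 | 11.0% |
| 2 | 1.39 | 16.6% |
| 3 | 1.13 | 25.8% |

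Simulation agrees: 10.6 to 25.7% for φ from 1.5 to 3.

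**3. AEs divided by 80 and tested as a percentage.** The test assumes variance m(1 − m)/80; the true variance is φm/80. The ratio is φ/(1 − m), and the rate is about 2 × [1 − Φ(1.96/√(φ/(1 − m)))]:

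| φ | m = 0.3 | m = 0.6 |
|---|---|---|
| 1 | 10.1% | 21.5% |
| 1.5 | 18.1% | 31.1% |
| 2 | 24.6% | 38.1% |
| 3 | 34.4% | 47.4% |

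Simulation gives 10.6 to 21.8% for Poisson counts and up to 47.5% at φ = 3. From a mean of about 1 AE per patient, the supposed proportion can exceed 100%.

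**4. Share of AEs with some feature, such as attribution to the device.** Assuming 30% of AEs have the feature and a mean of 0.5 to 2 AEs per patient, the rate is 5.0 to 5.1% with no within-patient correlation. It is 6 to 26% at intra-patient correlations of 0.3 to 1.

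**5. Device defects.** Two kits at each of seven centres (section 6.6.4 numbers centres 1 to 7) is about 14 kits, or 80/14 = 5.7 BioRoot patients per kit. A 5% risk per use would become 1 − 0.95^5.7 = 25% per kit, against 5% per syringe used once. A proportion per device thus means different things in the two arms.

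**The case against.** **The test is inferred.** A reader might take it that the plan prescribes chi-squared or Fisher for AEs. Section 7.7.6 does not; the link comes from a general rule limited to independent percentages. That is correct. But the synopsis extends the rule to safety criteria, and the plan offers no other rule for percentages.

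**A valid route exists in the plan.** Table 3 lists the number of AEs separately from the proportion of patients with at least one. As a quantitative variable, AEs per patient would go to Student, Welch or Wilcoxon under 7.7.3. In the scenarios above, Welch gives 3.9 to 5.1% and Wilcoxon 4.2 to 5.4%. This stands, although the word proportions in 7.7.6 points away from that route.

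**Inflation depends on assumptions.** Event totals keep the 5% level if Poisson, and the per-patient denominator is one possible reading. Both points stand.

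**Defects.** A reader might infer that the 5% level also fails for defects, or that no common denominator exists. The documents support neither. With equal risk per device, 80 syringes v 14 kits gives 1.6 to 3.0%. Per patient, for defect rates of 5 to 20%, the rate is 2 to 5% without correlation within kits. It rises to 7 to 14% at an assumed correlation of 0.3, and to 20 to 31% if a defect affects a whole kit. A common unit is available: section 6.2 gives 80 treated patients in each arm. It is simply not named.

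**Detail is left to a later statistical analysis plan.** Section 7.7 says so, and 7.7.9 has it drawn up before the first interim analysis. That makes the repair easy; it does not make the stated comparison valid.

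**Conclusion.** The point holds for the AE-level comparison and should be corrected. Under the plan's general rule for percentages, comparing proportions of AEs is not valid when a patient can contribute several events. The size is conditional on the assumed rates and dispersion: with 0.3 to 0.6 AEs per patient and 80 per arm, about 11 to 26% for overdispersed totals, and about 11 to 48% for AEs divided by patients.

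It would be wrong to read this as a failure of the whole safety analysis. The patient-level comparison in the same sentence is valid. For defects the finding is only that the unit is undefined and that kits and syringes are not like for like. The non-inferiority test, the sample size and the conclusion on PA1704 are unaffected, and no statistical stopping rule depends on these comparisons (section 7.7.8).

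**What to change.** In section 7.7.6, the matching synopsis paragraph and the statistical analysis plan:

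- Make patients with at least one AE the only tested AE proportion, reported as a risk difference with a 95% confidence interval.
- Describe the number of AEs without a test, or compare AEs per patient by a method valid for overdispersed counts: negative binomial, Poisson with robust variance, or the Welch or Wilcoxon test already in 7.7.3.
- For defects, keep the list and compare the number of treated patients with at least one defect at the filling session, in both arms. Note that BioRoot patients share kits.

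The cost is wording only; no extra data or patients are needed. It should be settled before the first interim analysis.
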